7.5.2.8 Clinical Global Impression Scale

The CGI (a tertiary endpoint) was developed for use in National Institute of Mental Health-sponsored clinical trials to provide a brief, stand-alone assessment of the clinician's view of the patient's global functioning prior to and after initiating a study medication ([Guy 1976](#)).

The CGI provides an overall clinician-determined summary measure that takes into account all available information, including knowledge of the patient's history, psychosocial circumstances, symptoms, behavior, and the impact of the symptoms on the patient's ability to function.

The Investigator will perform the CGI-Severity scale (CGI-S) at the Baseline Visit to rate the severity of a subject's condition on a 7-point scale ranging from 1 (normal, not at all ill) to 7 (among the most extremely ill subjects). The Investigator will also identify 3 target areas of improvement with the subject, which will be recorded in the source documents. To generate the targets, an open-ended question should be asked, such as "If this program of treatment works for you, what things do you hope you will be doing better?"

At Weeks 24 and 48 (or Early Termination), the Investigator will administer the CGI-Improvement (CGI-I) scale to assess the subject's overall improvement in the 3 target areas recorded at the Baseline Visit, using a 7 point scale ranging from 1 (very much improved) to 7 (very much worse). The CGI-S and CGI-I should be completed by a clinician experienced in the evaluation of patients with GNEM.

7.5.2.9 Creatine Kinase Levels

CK is a biochemical marker of muscle injury in many muscular system disorders. Most GNEM patients have some modest elevation of CK; in approximately 50% of patients CK levels are increased at least two-fold above the ULN. CK levels in serum (a tertiary endpoint) will be measured as indicated in the Schedule of Events ([Table 2.1](#)) to assess the degree of reduction associated with treatment.

7.5.3 Drug Concentration Measurements

The concentration of free SA in serum will be measured. At the Baseline Visit and each subsequent visit a serum sample will be collected prior to the morning dose of study medication (pre-dose) to assess trough levels of free SA.

The free, total, and bound urine SA levels (corrected for creatinine) will be measured. At the Baseline, and Week 16, 32, and 48 (or Early Termination) visits, first-morning void urine will be collected (pre-dose) to assess trough levels; the volume obtained will be recorded.

Collection and processing instructions can be found in the Laboratory Manual.

7.5.4 Urine Testing for ManNAc

An aliquot from the urine sample provided for the standard urinalysis testing will be analyzed for the presence of ManNAc at Screening, Baseline, and Week 16, 32, and 48 (or Early Termination) visits to detect noncompliance with prohibited medication restrictions.

Collection and processing instructions can be found in the Laboratory Manual.

7.5.5 Safety Measures & General Assessments

General assessments include medical history, demographics, height and weight. Safety will be evaluated by the incidence, frequency and severity of AEs and SAEs, including clinically significant changes from study baseline to scheduled time points in interval history, physical examinations, vital signs, clinical laboratory evaluations, suicidal ideation and behavior, and concomitant medications. Pregnancy testing (or pregnancy of partner, if needed) will also be conducted as appropriate. Refer to the Study Reference Manual for additional details on safety measures and general assessments.

7.5.5.1 Medical History

A detailed medical history will be obtained at the Screening Visit to solicit information on any prior or existing medical conditions that might interfere with study participation or safety. General medical information includes subject demographics (date of birth, ethnicity, and sex) and a history of major medical illnesses, diagnoses, and surgeries. The GNEM-specific medical history should elicit all major illnesses, diagnoses, and surgeries to date. Any relevant concomitant therapy, including physical/occupational therapy will be recorded.

7.5.5.2 Height and Weight

Height and weight will be captured at the Screening Visit and should be measured by the trained clinician administering the performance testing. A calibrated stadiometer must be used for all height measurements. Height should be measured in inches or centimeters without shoes with the subject standing on a flat surface. A calibrated scale must be used for all weight measurements. Weight should be measured in pounds or kilograms without shoes.

Height and weight data will be used to evaluate each subject's muscle strength and function using published normative data where available. The measurement obtained at the Screening Visit will be used for all derivations of percent predicted.

7.5.5.3 Interval History

The interval history is intended to record any signs, symptoms, or events (e.g. falls) experienced by the subject since the prior study visit that are not related to study procedure(s) performed at prior study visits or study drug. Interval history may include exacerbation or improvement in existing medical conditions (including the clinical manifestations of GNEM) that might interfere with study participation, safety, and/or positively or negatively impact performance of functional assessments. Interval history may identify under-reported AEs and will be collected at each study visit (except Screening).

7.5.5.4 Physical Examination

Complete physical examinations will be performed at Baseline, and the Week 24 and 48 study visits (or Early Termination). Physical examinations will include assessments

of general appearance; head, eyes, ears, nose, and throat; the cardiovascular, dermatologic, lymphatic, respiratory, GI, genitourinary, musculoskeletal, and neurologic systems.

The neurologic system examination will include assessments of cognition, cranial nerves, motor function, coordination and gait, reflexes, and sensory function. Brief physical examinations will be conducted at all other study visits and will include assessments of general appearance, cardiovascular and respiratory systems, and a focus on any presenting complaints. Clinically significant changes from baseline will be recorded as AEs.

7.5.5.5 Vital Signs

Vital signs will include seated systolic blood pressure and diastolic blood pressure measured in millimeters of mercury (mmHg), heart rate in beats per minute, respiration rate in breaths per minute, and temperature in degrees Celsius (°C). Vital signs measurements will be performed at every visit before any additional assessments are completed.

7.5.5.6 Clinical Laboratory Tests for Safety

The clinical laboratory evaluations to be performed in this study include a serum chemistry, complete blood count (hematology), and urinalysis; specific analytes are listed in [Table 7.5.5.6.1](#). Clinical laboratory testing will be performed at every visit. Blood and urine samples will be collected prior to administration of study drug; fasting is not required. Refer to the Laboratory Manual for additional details.

Table 7.5.5.6.1: Clinical Laboratory Assessments for Safety

Chemistry	Hematology	Urinalysis
Alanine aminotransferase (ALT)	Hematocrit	Appearance
Alkaline phosphatase	Hemoglobin	Bilirubin
Amylase	Mean corpuscular hemoglobin (MCH)	Blood pH
Aspartate aminotransferase (AST)	MCH concentration (MCHC)	Color
Bilirubin (direct and total)	Mean corpuscular volume (MCV)	Creatinine ²
Blood urea nitrogen (BUN)	Platelet count	Glucose
Calcium	Red blood cell (RBC) count	Hemoglobin
Chloride	Reticulocyte count	Ketones
Cholesterol (total)	Neutrophil count (absolute and %)	Leukocyte Esterase
Creatine kinase ¹	Lymphocyte count (absolute and %)	ManNAc ³
Creatinine	Monocyte count (absolute and %)	Nitrite
Gamma-glutamyl transpeptidase (GGT)	Eosinophil count (absolute and %)	Protein
Glucose	Basophil count (absolute and %)	Specific gravity
Lactate dehydrogenase (LDH)	White blood cell (WBC) count	Urobilinogen
Lipase	WBC differential	
Phosphorus		Pregnancy test (if applicable)
Potassium		
Protein (albumin and total)		*Special assessment
Sodium		Serum pregnancy test if a positive urine pregnancy test
Triglycerides		

¹ Also designated as PD variable (Section 7.5.2.9)

² Relevant to Drug Concentration Measurements (Section 7.5.3)

³ To screen for use of prohibited medications (Section 7.4.6.1)

If urinalysis detects protein, leukocyte esterase, blood or nitrite, microscopic examination will be conducted. The microscopic examination will consist of White Blood Cell (WBC), Red Blood Cell (RBC), Epithelial Cells: Squamous, Epithelial Cells: Transitional, Epithelial Cells: Renal Tubular, Hyaline Casts, WBC Casts, RBC Casts, Waxy Casts, Granular Casts, Calcium Oxalate Crystals, Uric Acid Crystals, Triphosphate Crystals, Yeast, Bacteria, Amorphous Urates, and Amorphous Phosphates.

Subjects who experience a SAE possibly or probably related to study drug or other AE of concern may, at the discretion of the Investigator (and/or medical monitor), have additional blood samples taken for safety laboratory tests.

Upon completion of protocol-specified laboratory tests, leftover blood and urine samples from each visit may be used for additional exploratory research, eg, biomarker research. The leftover samples from this study will not be used for genetic testing.

7.5.5.6.1 Volume of Blood to Be Drawn from Each Subject

During this study, it is expected that approximately 16 mL of blood will be drawn from each subject, at each required time point, regardless of gender or age. The amount of blood required for each sample type is presented in [Table 7.5.5.6.1.1](#). The amount of blood to be drawn for each assessment is an estimate, and may vary according to the instructions provided by the manufacturer or laboratory for an individual assessment. Samples indicated at the time point/period may be utilized for more than one assessment if the same type of tube is required (e.g. CK and serum chemistry).

Table 7.5.5.6.1.1: Volume of Blood to Be Drawn From Each Subject

Assessment		Sample Volume (mL)	Number of Samples	Total Volume (mL)
Safety	Chemistry ¹	7.5	8	60
	Hematology	3	8	24
PK	Sialic Acid	5	7	35
Total mL through study completion				119

¹ Includes CK, an efficacy variable

7.5.5.7 Pregnancy Testing

Female subjects of childbearing potential with a positive pregnancy test at Screening will not be enrolled in the study. Female subjects will have urine pregnancy tests at the Baseline visit, at 16-week intervals throughout the study (or Early Termination).

Additional pregnancy tests will be performed at any visit in which pregnancy status is in question. A serum pregnancy test will be performed in the event of a positive or equivocal urine pregnancy test result, or can be performed if pregnancy test by urine is not feasible.

Experience with UX001 in pregnant women is limited. The study drug may involve risks to a pregnant female or unborn baby which are currently unknown. Participants of child-bearing potential or with partners of child bearing potential who have not undergone a bilateral salpingo-oophorectomy and are sexually active must consent to use a highly effective method of contraception as determined by the site investigator from the period following the signing of the informed consent through 3 months after last dose of study drug. Examples of highly effective methods of contraception include oral hormonal contraceptives, patch hormonal contraceptives, vaginal ring, intrauterine device, physical double-barrier methods, surgical hysterectomy, vasectomy, tubal ligation or true abstinence (when this is in line with the preferred and usual lifestyle of the subject), which means not having sex for the duration specified above because the subject chooses not to.

7.5.5.7.1 Pregnancy in Subject or Partner

Pregnancies in subjects or partners must be reported within 24 hours of knowledge of the event to Ultragenyx or its designee. The Investigator must make every effort to follow the pregnancy of either subject or partner through resolution of the pregnancy (delivery or termination) and report the resolution to Ultragenyx or its designee. In the event of a pregnancy in the partner of a subject, the Investigator should make every effort to obtain the female partner's consent for release of protected health information. Refer to the Study Reference Manual for details on the reporting procedures to follow in the event of pregnancy.

7.5.5.8 Suicidal Ideation and Behavior

Prospective assessment of suicidal ideation and behavior is a regular part of development programs involving any drug being developed for any psychiatric indication, as well as for all antiepileptic drugs and other neurologic drugs with central nervous system activity (FDA Draft Guidance, 2012). The Columbia Suicide Severity Rating Scale (C-SSRS) is a standardized rating instrument used to assess the suicidal ideation and behavior in an at-risk population (Posner et al. 2011). To prospectively assess suicidal ideation and behavior, the C-SSRS will be administered by trained site personnel. The Baseline/Screening C-SSRS will be administered at the Screening and Baseline visits; the Since Last Visit C-SSRS will be administered at all subsequent visits. The responses to the questionnaire will be reviewed by site personnel during the study visit; if emergent suicidal ideation or behavior is indicated, the investigator should promptly evaluate the subject to ensure proper management and protection of subject safety.

7.5.5.9 Concomitant Medications

Concomitant medications will be reviewed and recorded in the subject's CRF at each study visit, beginning at the Screening visit. Medications (investigational, prescription, over-the-counter, and herbal) and nutritional supplements taken during the 30 days prior to Screening will be reviewed and recorded. At each subsequent visit, change in medications since the previous visit will be recorded. A discussion of concomitant medications is provided in Section 7.4.6.

7.5.5.10 Adverse Events

All AEs will be recorded from the time the subject signs the informed consent until 30 days after the last dose of study drug, or, if applicable, until the date the subjects signs the informed consent for the open-label extension study, UX001-CL302, whichever occurs sooner.

The determination, evaluation, reporting, and follow-up of AEs will be performed as outlined in Section 8.5. At each visit subjects will be asked about any new or ongoing AEs since the previous visit. Assessments of AEs will occur at each study visit.

Clinically significant changes from study baseline in interval history, physical and neurological examination findings, vital signs, weight, clinical laboratory parameters, and concomitant medications will be recorded as AEs or SAEs, if appropriate.

7.5.6 Appropriateness of Measures

The efficacy parameters to be evaluated in this study include clinical changes in muscle strength, subject mobility and function. The clinical assessments in the study employ standard performance measures used in other neuromuscular diseases and conditions that cause muscle weakness and impaired function. Based on results from Phase 2 studies and published studies ([Aitkens et al. 1989](#)), the study will focus on quantitative muscle testing. The strength of a set of muscle groups in the upper and lower extremities will be assessed by dynamometry, a form of quantitative muscle testing that uses a device with a strain gauge to measure force during a MVIC ([Sisto et al. 2007](#)). An interview-based measure designed to evaluate ability in GNEM patients (GNEM-FAS) will be administered in this study to support the clinical meaningfulness of changes in muscle strength. In addition, walking ability will be assessed using the 6MWT test, a test of endurance commonly used in clinical trials for various indications that has served as the basis for many product approvals.

The level of free SA in serum will reflect the absorption of and exposure of the muscles to SA during treatment. Serum CK level will be assessed as a measure of muscle injury throughout the study; a positive dose-dependent decrease in serum CK levels was observed in the UX001-CL201 Week 24 analysis. Unlike other myopathies, CK activities are mildly elevated or in the normal range for these patients. The mouse model of HIBM showed elevated CK levels that improved substantially on treatment ([Malicdan et al. 2009](#)).

The safety parameters to be evaluated in this study include standard assessments such as recording of medical history, AEs and SAEs, physical examination, neurological examination, vital signs, serum chemistry, and other routine clinical and laboratory procedures. In addition, symptoms of increasing muscle weakness and pain which are characteristic of myopathy will be recorded in interval histories. Suicidal ideation and behavior will be assessed using C-SSRS, a standardized rating instrument recommended in clinical trials of any investigational drug with potential neurological activity (FDA Draft Guidance, 2012).

7.6 Statistical Methods and Determination of Sample Size

The completeness of the data affects the integrity and accuracy of the final study analysis. Therefore, every effort will be made to ensure complete, accurate and timely data collection, and to avoid missing data. The procedures for handling missing, unused, or spurious data, along with the detailed method for analysis of each endpoint will be presented in the Statistical Analysis Plan (SAP); the information below is intended as a guide to planned analyses.

7.6.1 Determination of Sample Size

Based on the results of the Phase 2 study (UX001-CL201), approximately 80 subjects will be randomized in this Phase 3 study. This sample size will provide 90% power to detect a difference of about 5 kg in the UEC score change from baseline between the SA-ER treatment and the placebo groups, assuming a standard deviation of 6, and a two-sided alpha of 0.05.

7.6.2 Subject Information

Summaries and listings will be provided for all subjects who received at least 1 dose of study drug and provided at least 1 safety or efficacy evaluation. Subject disposition summaries will include the number of randomized subjects, the number of subjects receiving study medication, the number of subjects completing the study, and the reasons for discontinuation. Demographic variables include age, sex, and race.

7.6.3 Populations Analyzed

Primary Analysis Set: The primary efficacy set will include all randomized subjects with a baseline measurement and at least one post-baseline measurement. Each subject will be included in the treatment group assigned at randomization, regardless of the treatment received. This set will be used for the primary analyses of all efficacy endpoints.

Safety Analysis Set: The safety analysis set consists of all randomized subjects who receive at least one dose of study drug. This set will be used for the analyses of all safety endpoints.

Sialic Acid Analysis Set: The SA analysis set will consist of all randomized subjects with evaluable free serum SA levels or urine SA levels.

7.6.4 Efficacy Analysis

Baseline values for each endpoint will be defined as the last scheduled data collection visit before beginning treatment according to the Schedule of Events ([Table 2.1](#)).

Dynamometry, sit-to-stand test, weighted arm lift test, and 6MWT will be administered at the Screening visit to determine eligibility and introduce subjects to performance testing to minimize training effects and will not be used for analysis purposes.

Efficacy analyses will be based on the primary analysis set and will be stratified by gender. GEE analysis will be performed to compare the two treatment groups with respect to the changes from baseline of primary endpoint, secondary endpoints, and all tertiary efficacy endpoints. Baseline, gender, and geographic region will be included as covariates in the model. In general, randomly missing data for an individual subject will be treated as missing. The GEE method handles these cases appropriately. If a subject drops out following a decline in function, regardless of whether that is the reason listed for withdrawal, then it will be assumed that missing data are not missing at random and a single imputation rule will be used. This method will be the primary analysis method for all repeated measures endpoints.

The statistical analyses will be reported using summary tables, figures, and data listings. Statistical tests will be 2-sided at the $\alpha = 0.05$ significance level. All analyses and tabulations will be performed using SAS[®] or SPLUS. Continuous variables will be summarized with means, standard deviations, medians, minimums, and maximums. Categorical variables will be summarized by counts and by percentages of subjects in corresponding categories. The final analysis will be conducted at Week 48.

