STATISTICAL METHODS:

Sample Size:

Based on the results of the Phase 2 study (UX001-CL201), approximately 80 subjects will be randomized in this Phase 3 study. This sample size will provide 90% power to detect a difference of about 5 kg in the UEC score change from baseline between the SA-ER treatment and the placebo groups, assuming a standard deviation of 6, and a two-sided alpha of 0.05.

Data Monitoring Committee (DMC):

An independent and appropriately constituted DMC will act in an advisory capacity to monitor subject safety on a routine basis throughout the trial.

Analyses Sets:

Primary Analysis Set: The primary efficacy set will include all randomized subjects with a baseline measurement and at least one post-baseline measurement. Each subject will be included in the treatment group assigned at randomization, regardless of the treatment received. This set will be used for the primary analyses of all efficacy endpoints.

Safety Analysis Set: The safety analysis set consists of all randomized subjects who receive at least one dose of study drug. This set will be used for the analyses of all safety endpoints.

Sialic Acid Analysis Set: The SA analysis set will consist of all randomized subjects with evaluable free serum SA levels or urine SA levels.

Efficacy Analyses:

Baseline values for each endpoint will be defined as the last scheduled data collection visit before first dose according to the Schedule of Events (Table 2.1). Dynamometry, 6MWT, sit-to-stand, and weighted arm lift tests will be administered at the Screening visit to introduce subjects to performance testing to minimize training effects and will not be used for statistical analysis.

Efficacy analyses will be based on the Primary Analysis Set and will be stratified by gender. GEE analysis will be performed to compare the two treatment groups with respect to the changes from baseline for the primary endpoint, and all secondary and tertiary efficacy endpoints. Baseline will be included as a covariate in the model. This method will be the primary analysis method for all repeated measures endpoints.

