### 3.5 Stratification Factors

Subjects will be enrolled in the study and sequentially assigned an identification number. Approximately 80 eligible subjects will be randomized via an Interactive Web Randomization System (IWRS) and assigned in a 1:1 ratio to receive 6 g/day of SA-ER or matching placebo for 48 weeks. Randomization of subjects will be stratified by gender with a planned enrollment of no more than 60% of subjects of either gender.

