### 3.7 Determination of Sample Size

The design and analysis of this study is intended to provide sufficient data to evaluate clinical efficacy of SA-ER.

Based on the results of the Phase 2 study (UX001-CL201), approximately 80 subjects will be randomized in this Phase 3 study. This sample size will provide 90% power to detect a difference of 5 kg in the UEC score change from baseline using a t-test between the SA-ER treatment and the placebo group, assuming a standard deviation of 6, and a two-sided alpha of 0.05.

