#### 4.8 Potential Covariates

All models used for each individual clinical endpoint will incorporate the baseline value, gender and region as covariates. Region is comprised of two levels, one that combine all sites in North America, and the other one combines all sites in the rest of the world. Additional covariates may be used and the details will be included in the analysis model.

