## 8.7 Primary Efficacy Endpoint and Analysis

The primary clinical efficacy analysis will be the changes from baseline in UEC score over time for the SA-ER group compared with placebo based on bilateral strength recorded in the following muscle groups using a dynamometer: gross grip, shoulder abductors, elbow flexors, and elbow extensors. The UEC is derived from the sum of the muscle groups. Each muscle group value will represent the average of the right and left total values (measured in kg).

The comparison of the two treatment groups will be based on the changes from baseline over time in mean UEC score between SA-ER and placebo using the week 48 ls-means from GEE repeated measures analysis with baseline, gender, and region as covariates. Region is considered as a covariate to account for the heterogeneity of the disease observed in some European countries and Israel relative to North American patients.

The imputations method described in Section 7.1 will be used to estimate the change in strength for dropouts. Sensitivity analyses will also be performed as described in Section 8.1.

In addition, the primary analysis will be repeated in the Per Protocol population.

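### Screening strength and performance tests, collected before randomisation, are left out of the efficacy models; adding them as a covariate would give a modest precision gain of uncertain size

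*Protocol*

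**What the plan says.** Protocol Table 2.1 schedules dynamometry, the six-minute walk, sit-to-stand and weighted arm lift at Screening for every subject. Section 7.5.1.2 puts Baseline 7 to 28 days later and allows randomisation only once eligibility is confirmed, so these values precede randomisation.

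Protocol 7.6.4 then says that the Screening tests determine eligibility and "introduce subjects to performance testing to minimize training effects and will not be used for analysis purposes". The synopsis gives the same purpose and the same exclusion: "minimize training effects and will not be used for statistical analysis".

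SAP 4.8 fixes the covariates: "All models used for each individual clinical endpoint will incorporate the baseline value, gender and region as covariates". SAP 8.7 applies them to the primary endpoint through the Week 48 least-squares means of a "GEE repeated measures analysis with baseline, gender, and region as covariates".

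Three other SAP statements bear on this. Section 1 gives the SAP precedence over the Protocol on analysis methods. Section 4.8 allows further covariates without naming any. Section 5.1 defines baseline as the last assessment on or before the date of first dose, without excluding Screening.

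**The concern.** UEC change is measured from a single Week 0 session, and the error in that session enters the change at all six post-baseline visits. Adjusting for the Week 0 value removes part of it. A second pre-treatment measurement of the same quantity would remove more, and one is already collected.

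The stated reason for setting it aside is training. That argues against Screening as the reference point for change, since a learning shift would be mistaken for change. As a covariate, a learning shift is common to both arms and independent of assignment. At stake is precision for UEC, for two of the three key secondary endpoints (LEC and knee extensors), and for sit-to-stand, arm lift and six-minute walk. The GNEM-FAS is not done at Screening and is unaffected.

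**Working it through.** **1. The plan's own figure.** SAP 3.7 states that "approximately 80 subjects will be randomized in this Phase 3 study", and "This sample size will provide 90% power to detect a difference of 5 kg in the UEC score change from baseline using a t-test", "assuming a standard deviation of 6, and a two-sided alpha of 0.05". Allocation is 1:1 (SAP 3.5), so 40 per arm. The standardised effect is 5 / (6 × √(2/40)) = 5 / 1.342 = 3.727. Power is Φ(3.727 − 1.960) = 96.1% by the normal formula and 95.7% by the exact t, not 90%. On these inputs 90% needs 32 per arm (exact t: 90.7%; 31 per arm gives 89.8%), or 64 in total. The figure of 80 would follow from 64 / 0.8, a 20% loss allowance that the documents do not state.

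**2. Model for the gain.** Let a subject's true pre-treatment UEC have between-subject variance τ², let each session add independent error with variance σ², and let true change to Week 48 have variance 36 − 2σ², so that the SD of observed change stays at 6 kg. The residual variance at Week 48 is then

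- Week 0 only: 1/(1/τ² + 1/σ²) + (36 − 2σ²) + σ²
- Week 0 and Screening: 1/(1/τ² + 2/σ²) + (36 − 2σ²) + σ²

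Only the 6 kg comes from the documents. τ = 15 kg and σ = 2, 3 or 4 kg are assumptions. The last column gives Screening twice the error variance, replacing 2/σ² by 1.5/σ².

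| σ (kg) | Week 0 only | plus Screening | reduction | reduction, Screening twice as noisy |
|---|---|---|---|---|
| 2 | 35.93 | 33.98 | 5% | 4% |
| 3 | 35.65 | 31.41 | 12% | 8% |
| 4 | 34.94 | 27.73 | 21% | 14% |

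Example at σ = 3: 1/(1/225 + 1/9) + 18 + 9 = 8.65 + 27 = 35.65, and 1/(1/225 + 2/9) + 27 = 4.41 + 27 = 31.41.

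**3. How far the assumptions drive this.** At σ = 1 kg the reduction is 1.4%. With τ = 8 kg the three reductions are 5%, 11% and 17%; with τ = 20 kg they are 5%, 12% and 21%. So σ matters far more than τ. As a cross-check, if Screening, Week 0 and Week 48 share one correlation ρ, the reduction is ρ²/(1+ρ)²: 5.3% at ρ = 0.3, 11.1% at 0.5, 19.8% at 0.8, with a limit of 25%. The attainable range is therefore about 0% to 25%.

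**4. Power.** Exact t, 40 per arm with full retention, the variances in step 2, and 75 or 74 residual df:

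| True difference | σ = 2 | σ = 3 | σ = 4 |
|---|---|---|---|
| 5 kg (design) | 95.7 → 96.6% | 95.9 → 97.6% | 96.2 → 98.7% |
| 4.69 kg | 93.2 → 94.4% | 93.4 → 95.8% | 93.9 → 97.6% |
| 3.44 kg | 71.7 → 74.0% | 72.0 → 77.3% | 72.9 → 82.2% |

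The 4.69 and 3.44 kg figures are the Phase 2 Week 48 differences between 6 g and 3 g per day in Protocol 5.2.3, for subjects walking more than 200 m and for all subjects.

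**5. Validity.** Week 48 ANCOVA was simulated as a stand-in for the GEE: 80 subjects, no treatment effect, a mean learning shift of 2 kg varying between subjects with SD 1 kg, 6,000 trials per setting. With Screening added, the treatment estimate stayed unbiased (largest mean error 0.022 kg) and type I error was 4.9% to 5.2%. The variance of the estimate fell by 0.7% to 20.2% as the share of change variance due to measurement error rose from 10% to 100%.

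**The case against.** The planned model is valid and conventional, and using a familiarisation session only for training and eligibility is a legitimate choice. That stands, and it is why this is not an error.

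The size is also open to challenge. At σ = 4 kg, measurement error makes up 32 of the 36 units of change variance, which leaves a true-change SD of only 2 kg in a disease that the Protocol calls variable between patients. The Protocol also acts against noise through trained assessors, three attempts with the highest value used, and a reproducibility criterion for elbow flexors. A first session may be noisier than the second, which is why the last column in step 2 is given. All of this stands and points towards the lower part of the range.

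The 3.44 kg row flatters the gain. It is not a placebo contrast, and it covers all Phase 2 subjects. The subset behind 4.69 kg is closer to this trial's entry criterion, although that too is a dose comparison.

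Three stronger readings are tempting and not supported. A reader might infer that the whole plan bars Screening values. The exclusion is in the Protocol only; the SAP, which governs methods, does not repeat it and permits additional covariates. A reader might infer a known loss of up to a fifth of the variance, recoverable at no cost. No document gives UEC reliability, and the change costs a degree of freedom and a missing-value rule. A reader might infer that the trial is underpowered or biased without the covariate. On the plan's own inputs power is about 96%, and the planned comparison is unbiased in this respect.

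**Conclusion.** The point holds as an efficiency improvement. The Protocol's reason supports keeping Screening out of the baseline but not out of the model. Under assumed UEC noise of 2 to 4 kg, Week 48 residual variance would fall by about 5% to 21% (4% to 14% with a noisier Screening session), equivalent to roughly 85 to 101 subjects instead of 80 (80 × 35.93/33.98 and 80 × 34.94/27.73). At 1 kg noise the gain is close to nothing.

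Power rises by about 1 to 2.5 points at 5 kg, 1 to 4 points at 4.69 kg, and more at smaller effects. These figures assume full retention and a Week 48 ANCOVA in place of the GEE. No gain has been calculated for LEC, knee extensors, sit-to-stand, arm lift or six-minute walk.

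One inconsistency needs settling whatever is decided. If a Week 0 value is missing, SAP 5.1 could let a Screening value become baseline, which Protocol 7.6.4 excludes.

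**What to change.** Before unblinding:

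- In SAP 4.8 and 8.7, name the Screening value of the same endpoint as an additional prespecified covariate for UEC, LEC, knee extensors, sit-to-stand, arm lift and six-minute walk. Keep Week 0 as the baseline for change.
- State that a missing Screening value is filled from the subject's Week 0 value, blind to arm.
- Reword Protocol 7.6.4 and the synopsis to say that Screening values are not used as baseline but may enter as a covariate.
- Align SAP 5.1 so that a Screening performance test cannot become baseline.

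The cost is one degree of freedom out of about 75, one missing-value rule and a few sentences in each document. No new data are needed.
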